Current data demonstrates that some degree of neurobehavioral disability is present on over 50% of survivors of cardiac surgery in the newborn period. Indeed, neurodevelopmental disability is now recognized as the most common complication of critical CHD (i.e. those patients requiring cardiac surgery in infancy) and has the most negative impact on quality of life, academic performance and opportunity for independence as an adult. Regardless of their origin, neurodevelopmental problems adversely affect learning and the attainment of academic, social, and vocational skills. Ultimately they undermine mental health and employment opportunities in adulthood. There is a wealth of disturbing data documenting the impact of neurodevelopmental deficits among children and adults affected by CHD. The need for special and rehabilitative services results in significant costs to the patients' families and to society. A potential benefit of the study is a reduced incidence of neurobehavioral disability leading to lower health care costs for society.

9.4.4 Risk-Benefit Assessment

Risk-Benefit Ratio:

There are significant potential benefits to the mother and fetus including prolongation of pregnancy, and improved brain development, with a reduction in peri-operative white injury leading to better long-term neurodevelopmental outcomes. Previous studies indicate that maternal progesterone therapy during the third trimester is associated with only a minor increase above minimal risk.

As outlined above, there is a possibility of collateral benefit from participation in the MRI assessments, however because of the potential need for sedation, this is a greater than minimal risk study with prospect for collateral benefit (Subpart D category §46.406 or §50.53).

9.5 Recruitment Strategy (or Case Ascertainment)

Subjects will be recruited from the Cardiac Center at CHOP. Eligible mothers and with a fetus with a prenatal diagnosis of CHD, who are followed by the Fetal Heart Program, will be recruited in person during a prenatal visit.

We plan to enroll sufficient patients to have 80 evaluable patients (40 per treatment group) at the 18 month neurodevelopmental testing. Based on known clinical outcomes for this patient population and experience with other studies with similar follow-up plans, we estimate a 5% early mortality and a further 20% attrition from all causes between hospital discharge and the 18 month evaluation. There may also be dropout prior to birth for a variety of reasons: fetal death, intolerance of therapy, withdrawal from study. We do not have accurate data to estimate this loss. We anticipate needing to enroll 110-130 patients to have a sufficient cohort at 18 months (40 per treatment group). We will use the IRB approved Cardiac Center Research Intro Sheet. This sheet is given to families in CICU and families followed by the Fetal Heart program at CHOP and lists all the studies in the Cardiac Center that recruit pre-operatively. [See current version attached in appendix section]. In addition, we plan to develop a study specific brochure similar to that used in the OPPTIMUM trial (attached in appendix), which we will submit for IRB approval.

9.6 Informed Consent/Accent and HIPAA Authorization

[name] and/or one of the research nurses will approach eligible families in person during a prenatal visit or upon admission to CHOP and ask their permission to review the research study. If families are willing, the following informed consent process will be initiated in order to assure subjects comprehend the purpose of the study, the study procedures, and the risk-benefit profile.

1. The research protocol will be reviewed verbally.
2. The consent form document will be reviewed.
3. The HIPAA authorization form will be reviewed.
4. Time will be provided for questions and decision making. There will be ongoing discussion with the parents to give them adequate time to consider participation.

[name] and/or one of the research nurses will approach eligible families in person during an outpatient visit or upon admission to CHOP and ask their permission to review the consent addendum. If families are willing, the following informed consent process will be initiated in order to assure subjects comprehend the purpose of the consent addendum, the additional study procedures, and the risk-benefit profile.

1. The research protocol will be reviewed verbally.

2. The consent addendum form document will be reviewed.
3. Time will be provided for questions and decision making.

9.7 Payment to Subjects/Families

9.7.1 Reimbursement for travel, parking and meals

At the time of both fetal brain MRIs, mothers will be reimbursed for travel, parking, need for babysitting, and meals. This will average between \$130 (local)-\$900 (outside the tristate needing hotel and airfare) based on where mothers reside during study period.

At the 18-month follow-up families will be reimbursed for travel, parking, need for babysitting, and meals. We have budgeted \$425-500 on average per family based on a range of \$190 for families coming by car with no hotel stay (70% referral base), \$600 for families coming by car with one night hotel stay or the need for round trip limo service (13% of referral base) to \$1300 for families coming by air with one-two hotel night stay (17% of our referral base).

9.7.2 Payments to parent for time and inconvenience (i.e. compensation)

Upon completion of each fetal brain MRI each mother will be given a \$50.00 gift card to compensate for time and inconvenience.

At the 18 month follow-up the parent will receive a \$50.00 gift card to compensate for time and inconvenience.

9.7.3 Gifts

At the 18-month follow-up the child will receive a book or small toy as a token of appreciation.

10 PUBLICATION

Any publication or presentation of the data will be done in a de-identified manner and under the guidance of [name], Principle Investigator.

Section 5.1.2 Post-Natal Medical Record Review

BIRTH

Date of Birth

Gender

Location of Birth

Gestational Age

Mode of Delivery

Apgar Scores

Weight at Birth

Length at Birth

Head Circumference at Birth

Adverse Events at delivery [Seizures, arrest, intubation, PGE]

INPATIENT ADMISSION(s)

Date of Admission

Medical Record Number

Diagnosis: CHD

Genetic Anomaly

Extra-Cardiac Anomaly

Data from clinical genetic consult(s)

Daily Weight

Daily Feeding Status

Daily Lowest Diastolic Blood Pressure

Daily Arterial Blood Gas [lowest PO₂, lowest PCO₂, lowest pH, and highest pH]

Type and duration of mechanical ventilation

Type and duration of intrathoracic catheters

Type and duration of intracardiac lines

Daily Events [NeuroCardiac Research Program database daily event code list]

Date of Surgery

Weight at Surgery

Surgical Procedure

Surgeon

Number of CPB Runs

CPB Time(s)

DHCA Time(s)

Cross Clamp Time(s)

Cooling Time(s)

Rewarming Time(s)

MUF

NP Temperature
Baseline Hematocrit
Hematocrit on CPB
Hematocrit following modified ultrafiltration
Hematocrit on admission to CICU
Anesthesiologist
Arterial Blood Gas 5 minutes after Commencement of Bypass
Blood Product Usage
Medication Usage
Cardiac Arrest Events
Reoperations
ECMO/VAD
Delayed Sternal Closure
Death
Date of Death
Date of Discharge
Cardiologist

OUTPATIENT

Events including procedures between discharge from neonatal surgery and 18month follow up

Statistical Analysis Plan
Randomized Trial of Maternal Progesterone Therapy to Improve
Neurodevelopmental Outcomes in Infants with Congenital Heart Disease.

J. [name], Principal Investigator
[name], PhD, ScD, Statistician

ClinicalTrials.gov identifier (NCT number): [NCT02133573](#)

Sponsor: Children's Hospital of Philadelphia

Version Date: 3/7/2022

Design: Randomized phase II 2-arm trial design

Control: Vaginal lubricant, twice a day

Intervention: Vaginal gel, 90mg twice a day

Consort Diagram: Per recommendations. <http://www.consort-statement.org/consort-statement/flow-diagram>

Primary Endpoint

The primary endpoint is the Motor Scale of the Bayley-III at 18 months of age.

Secondary Endpoints (Pre-specified in the protocol)¹

Secondary endpoints pre-specified in the protocol are:

1. Developmental (Bayley-III at 18 months of age)
 - a. Cognitive Scales
 - b. Language Scales
 - c. Fine motor score
 - d. Gross motor score
 - e. Receptive Communication
 - f. Expressive Communication
2. Adherence to study protocol
 - a. Progesterone regime (Average adherence by medication return and by diary)
 - b. Complete pre- and post-natal MRI's
 - c. Complete 18-month neuro-developmental evaluation
3. MRI-based
 - a. Total maturation score (TMS) on Pre-operative MRI
 - b. Brain volumes on Preoperative MRI:
 - i. Whole Brain
 - ii. Cerebellum
 - c. White Matter Injury
 - i. Volume on early post-natal brain MRI
 - ii. Volume on early post-operative brain MRI
 - iii. Volume change from pre-operative to post-operative brain MRI.

‘Secondary’ endpoints (Post Protocol) As clinical practice and research findings regarding progesterone use during pregnancy evolved over the course of accrual to the trial, these new secondary endpoints were identified. They were prespecified prior to closure of the database, and while the principal investigator and research team, other than [name] and [name] (statistical analyst), were blinded. They include;

1. Fetal Variables: Fetal echocardiogram and OB ultrasound Doppler flows (umbilical artery, uterine artery, middle cerebral artery, oligohydramnios, fetal growth restriction (BW < 10th percentile))
2. Maternal Complications: (gestational hypertension, preeclampsia, abruption, , gestational DM, maternal tobacco use, maternal hypothyroidism)

¹ We anticipate the trial resulting in at least two publications related to endpoints. In advance of seeing the unblinded data we anticipate a publication describing in depth results related to the primary endpoint and adherence. A brief description of key MRI-based endpoints may be included. A second publication will focus on MRI-based endpoints.

3. Impaired maternal-fetal environment (presence of 1 or more of gestational hypertension, preeclampsia, gestational DM, maternal tobacco use, maternal hypothyroidism)
4. Delivery Complications (abruption, post-partum bleeding, DVT/PE, perinatal mood/anxiety disorder, wound complications (infection, breakdown))
5. Postmenstrual age of neonate at time of birth,
 - a. Categorical: born earlier than 37 weeks postmenstrual age (PMA)
 - b. Continuous: PMA
6. Type of Delivery (Vaginal, Elective C-section, Emergent C-section)
7. Birthweight (BW), absolute and as Z-score
8. Placental descriptors: (placental weight (PW), PW < 10th percentile, ratio of BW to PW, presence of infarction, fetal vascular malperfusion, maternal vascular malperfusion, fetal vascular thrombi).
9. Brain growth and development. Trajectories of total and regional brain volumes and TMS from fetal to first post-natal MRI,
10. Post-operative seizures
11. Microhemorrhage and infarction
12. Age at post-operative MRI
13. Operative management variables (Cardiac operation during first admission y/n, age at first operation, cardiopulmonary bypass (CPB) y/n, weight at first operation, Clancy class, , deep hypothermia circulatory arrest (DHCA) time, Total support time (TST), antegrade cerebral perfusion time, need for extracorporeal membrane oxygenation (ECMO), additional operations with CPB, additional TST, additional DHCA)
14. Mortality (in-hospital, on-study and post-study)
15. Length of stay and selected complications for first surgical admission
16. Weight, length and HC at 18 months, absolute and as WHO percentile and Z-score

Intention to Treat Principle Unless otherwise specified, all analyses are conducted on an ‘as-randomized’ basis, irrespective of adherence to treatment. This analysis follows the intention to treat principle pre-specified in the protocol.

Descriptive Statistics (Intention to treat cohort)

1. Analyses will be done for the overall cohort as well as by primary cardiac diagnosis (HLHS, TGA, Other).
2. Baseline characteristics of mother: Using descriptive statistics (as appropriate, means median, number of subjects, proportion, standard deviation (SD), interquartile range (IQR)) to summarize demographic (Age of mother, race, ethnicity, education level of parents, clinical characteristics of mother) and clinical characteristics (Primary cardiac diagnosis, time to surgery, whether surgery was carried out) of the study cohort overall and by arm. Assess rates of missing data in baseline characteristics.
3. Determine rates of completion of primary endpoint of the study by arm. Describe causes of attrition including death (by arm). Kaplan-Meier plots of time-to-death by arm while on-study.
4. Characteristics of neonate. Type of birth (vaginal, emergency cesarean, planned cesarean), complications of pregnancy, progesterone level in cord blood, postmenstrual age of neonate, birthweight, sex, genetic anomaly, apo-lipoprotein E (*APOE*) genotype
5. Primary & secondary outcomes. These outcomes will be described using summary statistics, and for continuous variables, graphically to visualize the distribution, overall and by arm.

6. Genetic anomalies. The protocol pre-specified inclusion of 22q11 individuals. Additional anomalies as genomic information has evolved will be described. Subjects will be classified as Abnormal, Suspect, or Normal based on examination by a dysmorphologist and genetic testing (WES, microarray, and other clinical testing). Subjects with 22q11 deletions will be classified as Abnormal.

Efficacy Analysis

1. *Primary Endpoint (Motor Scale, Bayley III)*. The analysis will use a two-sided two-sample T-interval (estimation) or T-test (hypothesis testing). The confidence level will be set at 90% and the Type I error at 10%.
2. Normality will be assessed. A transformation, or alternatively a non-parametric test, will be used as appropriate.
3. Sensitivity of results to diagnosis group will be assessed by including diagnosis group as a stratification variable in a linear regression model.
4. *Continuous Secondary Endpoints* using the same analysis as the primary endpoint:
 - a. Cognitive and Language Scales (Bayley III)
 - b. TMS
 - c. Brain volumes
 - d. WMI volumes
 - e. PVL volumes
 - f. Adherence to study drug
5. *Binary Secondary Endpoints* will use an exact binomial confidence interval to estimate differences between groups and will be tested using Fisher's Exact test. The confidence level will be set at 90% and the Type I error at 10%. Binary outcomes include
 - a. Presence of WMI pre- and post-operatively
 - b. Completion of MRIs
 - c. Completion of Bayley III at 18 months
6. *Per Protocol and As Treated*
 - a. The analyses of the primary and secondary endpoints described above will be repeated with alternatives to the intention to treat cohort.
 - b. A 'strict' *per protocol* analysis will be used, considering only those subjects who were eligible for the study and who received the treatment as specified in the protocol. This analysis will consider only those subjects who completed at least 90% of their doses at the time of study-based discontinuation (pre-planned at XX weeks or due to earlier labor and delivery). Adherence will be measured in two ways (1) number of medication doses returned and (2) mother's diaries of medication use. Differences in the two measures of adherence will be described.
 - c. As a sensitivity analysis, a 'relaxed' *per protocol* analysis will follow (a) but use completion of 80% of doses instead of 90% of doses, as the cut-off.
 - d. An *as treated* analysis will consider subjects based on their 'dose of progesterone' based on their assignment to control or intervention arm, as well as adherence to study drug in the progesterone arm. In this case we will include dose as a continuous covariate in a regression model, using linear regression for continuous outcomes or logistic regression for binary outcomes. We will assess interactions between dose and treatment arm. This analysis will estimate the effect of the treatment intervention conditional on different levels of adherence to study medication.

7. *Modeling to Adjust for Covariate Imbalance.* Linear or logistic regression analyses of the primary and secondary outcomes will be carried out with adjustment for baseline covariates of fetal brain maturation and development. The covariates will include type of CHD (primary cardiac diagnosis), race, ethnicity, maternal education and socioeconomic status, presence of 22q11 deletions, other identified genetic anomalies and (*APOE*) genotype.
8. Missing data and truncation by death
 - a. In sensitivity analyses, multiple imputation will be used to impute missing outcome data using baseline covariates. Results will be compared to the primary analysis using the complete data.
 - b. Some subjects will have missing data for the 18-month endpoint due to truncation by death. In sensitivity analyses, we will assess the impact of this source of missingness using principal stratification.
9. Subgroup analyses of Primary & Pre-specified Secondary Endpoints:
10. Primary cardiac diagnosis
11. With versus without 22q deletions
12. With versus without any genetic anomaly
13. Males versus Female infants
14. Subjects undergoing surgical repair or not
15. With/without impaired maternal-fetal environment as defined above

Safety Analysis

All subjects the study at will be included in the safety analysis. The frequencies of adverse event (AE) by type, body system, severity and relationship to study drug will be summarized for both the mother and the neonate. Serious adverse events (SAE), if any, will be described in detail. AE incidence will be summarized along with the corresponding exact binomial 95% two-sided confidence intervals.

Further analyses anticipated for additional paper(s)

Using linear regression, we will assess the association between the neurodevelopmental outcomes with:

- 1) MRI findings (microhemorrhage, gray and white matter volumes, white matter injury (WMI) presence and volume, infarction, volume and growth trajectory) to neurodevelopmental (ND) outcomes
- 2) post-operative seizures
- 3) maternal complications and baseline clinical variables including diabetes, hypertension, smoking status, pre-eclampsia, hypothyroidism
- 4) placental findings
- 5) impaired maternal-fetal environment

Using regression techniques, including logistic regression for white matter injury (WMI) and competing risk time-to-event analyses (length of stay) with death as a competing risk), we will assess the association between the outcome (WMI, length of stay) and

- 1) maternal complications and baseline clinical variables
- 2) placental findings
- 3) trajectories of brain growth

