3.1.2 In Utero Treatment Phase

After informed consent is obtained, the subject will undergo baseline evaluation including medical history review, physical examination, obstetric ultrasound, fetal echocardiography, and fetal brain MRI. Maternal and paternal blood samples will be obtained. Progesterone levels will be assessed in the mother. Serum samples will be banked for later assessment of progesterone metabolites and biomarkers. The maternal and paternal samples will be used for genetic testing. Subjects will be randomized to study drug or placebo. For scheduling reasons, off site SD initiation may occur. After randomization, the subjects will return for routine prenatal visits every 2 weeks until 36 weeks GA and weekly thereafter. Obstetric ultrasound and fetal echocardiography will be performed every 4 weeks and as clinically indicated. Maternal blood tests will be repeated every 4 weeks. Fetal brain MRI will be obtained at 34-36 weeks GA. The study drug will be continued until 39 weeks GA, the onset of spontaneous labor if prior to 39 weeks GA, or the time of induction of labor or cesarean section for maternal or fetal health concerns. At the time of delivery, maternal and cord blood samples will be obtained. A portion of the placenta will be obtained.

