- Head, Face and Neck: Cerebellum, choroid plexus, cisterna magna, lateral ventricles, midline falx, cavum septi pellucidi, third ventricle, corpus callosum, posterior fossa, cerebellum, transcerebellar diameter (in centimeters), profile, nose, nasal bone, orbits, lips and palate.
- Chest-Heart: Four-chamber view, outflow tracts, situs, fetal heart rate and rhythm.
- Abdomen: Stomach (presence, size and situs), kidneys, bladder, umbilical cord insertion into the fetal abdomen, umbilical cord vessel number.
- Spine: Cervical, thoracic, lumbar and sacral spine.
- Extremities: Legs and arms (presence or absence). Femoral and humeral length in centimeters. Other long bone lengths will be obtained as clinically indicated.
- Genitalia (male, female, ambiguous).

Fetal Biometry at Repeat Examination: (ultrasound for growth to be performed at 4 week intervals)

- BPD, HC, FL, HL, AC, EFW.
- Fetal presentation.
- Amniotic fluid index and/or amniotic fluid deepest vertical pocket.
- Placental position (placental position at the initial evaluation may not correlate with its location in the third trimester).

- Maternal cervix (cervical length will be measured transabdominally or transvaginally at each sonographic evaluation until 32 weeks gestation) and presence, location and size of uterine and adnexal masses.

Doppler Ultrasonography:

Doppler color flow mapping with reduced color scale will be used to identify the ductus venosus (DV) and the middle cerebral artery (MCA) and average color scale to locate the umbilical artery (UA) and maternal uterine arteries (UtA). Pulsed- wave Doppler will be used to determine blood flow velocities of the UA, UtA, DV and MCA. The peak systolic velocity, peak diastolic velocity, mean velocity, systolic to diastolic ratio (SD), pulsatility index (PI) resistive index (RI) and UA PI/MCA PI with a mixture from stable signals during fetal apnea will be obtained for each of the aforementioned vessels at the initial evaluation at 24-28 weeks and then every 4 weeks.

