5.2.3 Fetal Cerebral Blood Flow

MCA Flow Velocities and Pulsatility Index

Doppler color flow mapping with reduced color scale will be used to identify the circle of Willis and the MCA. Pulsed-wave Doppler will be used to determine blood flow velocities in the UA, ductus venosus (DV) and MCA. The peak systolic velocity, peak end- diastolic velocity, and time averaged mean velocity are calculated on three consecutive samples during fetal apnea, and the results averaged. The pulsatility index (PI), a measure of vascular resistance in the circulatory bed downstream from the point of Doppler sampling will be calculated according to the equation, $PI = (\text{peak systolic velocity} - \text{end diastolic velocity})/\text{time averaged mean velocity}$. The ratio of UA-PI to MCA-PI will be designated the U/C-PI ratio. PI measurements of the aforementioned vessels will be converted to gestational age-based Z-scores to allow comparisons between the treatment and control group with previously published normal values.

Fractional Moving Blood Volume

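### The Doppler-flow and birthweight endpoints have planned pre-treatment counterparts that the SAP's covariate-adjusted model omits, and the scans that form the Doppler endpoint are not named

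*SAP*

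**What the plan says.** **Endpoints.** In the SAP's list of secondary endpoints added after the protocol, item 1 begins "Fetal Variables: Fetal echocardiogram and OB ultrasound Doppler flows (umbilical artery, uterine artery, middle cerebral artery" and goes on to oligohydramnios and growth restriction. It names vessels, but no scan, gestational window or summary across scans. Item 7 is "Birthweight (BW), absolute and as Z-score".

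**Baseline counterparts.** Protocol 3.1.2 describes the baseline work-up before it mentions randomization: "the subject will undergo baseline evaluation including medical history review, physical examination, obstetric ultrasound, fetal echocardiography, and fetal brain MRI". Under 5.2.1, velocities and indices including PI "will be obtained for each of the aforementioned vessels at the initial evaluation at 24-28 weeks and then every 4 weeks", and the vessels include the umbilical, uterine and middle cerebral arteries. The same section puts EFW in the biometry of the initial examination. Section 5.2.2 plans Doppler with fetal echocardiography for all patients at enrollment and four-weekly afterwards. Section 5.2.3 adds that "PI measurements of the aforementioned vessels will be converted to gestational age-based Z-scores", in part so that the arms can be compared.

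**Models.** SAP Efficacy Analysis item 7 plans adjusted regressions of the primary and secondary outcomes. "The covariates will include type of CHD (primary cardiac diagnosis), race, ethnicity, maternal education and socioeconomic status", followed by 22q11 deletion, other genetic anomalies and *APOE* genotype. No baseline Doppler value and no fetal size measure appears. The other models use diagnosis group (item 3) or dose (item 6d). Item 4, which gives named continuous secondary endpoints the same t-based analysis as the primary, names neither Doppler flow nor birthweight.

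**The concern.** When an outcome has a pre-treatment measurement of the same quantity, or a close relative of it, that measurement is often among the strongest available predictors. Leaving it out keeps stable differences between fetuses in the error term.

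The trial's population makes such differences likely. Protocol 1.5.3 reports that cerebrovascular resistance depends on the lesion: lower than normal in HLHS, and significantly higher in tetralogy of Fallot than in HLHS. The randomization strata are TGA, HLHS and other CHD, so tetralogy sits inside the mixed third stratum and a stratum term cannot separate it from the other lesions there. The fetus's own baseline PI can capture part of that variation. Protocol 1.5.5 and 1.5.6 likewise report more growth restriction in CHD pregnancies, which makes early fetal size a natural covariate for birthweight.

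The second gap is that the Doppler endpoint has no stated time point or summary. The measurement schedule includes a scan taken before any study drug, on which no treatment effect is possible, and the SAP does not say that this scan is kept out of the outcome. At stake are the width of the intervals for these endpoints and an open choice of scan at the time of analysis.

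**Working it through.** **Step 1. Reproduce the plan's own precision figure.** The documents give no precision figure for Doppler or birthweight. Their basis for continuous outcomes is Table 1 in Protocol 6.4: the half-width of a two-sided 90% t-interval.

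Half-width = t(0.95, 2n − 2) × SD × √(2/n)

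- n = 40 per arm: 0.372 SD; × 15 = 5.6 Bayley points. The table says 0.372 and 5.6.
- n = 50 per arm: 0.332 SD; × 15 = 5.0. The table says 0.332 and 5.0.

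The formula reproduces the plan's figures.

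**Step 2. Inputs for the fetal and birth endpoints.**

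- n = 60 per arm: the number Protocol 3.3.2 expects at the post-natal MRI, used here as a stand-in for dyads with fetal and birth outcomes. Planned enrollment of 110-130 gives 55-65 per arm.
- Confidence level 90%, as in the SAP.
- Correlation r between baseline and outcome: **not in the documents**. Assumed over 0.2 to 0.7. It need not be the same for PI against later PI as for EFW against birthweight.

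**Step 3. Interval with and without the baseline value, one post-treatment measure.**

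Unadjusted: t(0.95, 118) × √(2/60) = 0.303 SD.

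Adjusted: t(0.95, 117) × √(2(1 − r²)/60).

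| r | Variance removed (r²) | Adjusted half-width (SD) | Narrower by | Unadjusted n per arm for the same width, 60/(1 − r²) |
|---|---|---|---|---|
| 0.2 | 4% | 0.297 | 2% | 62.5 |
| 0.3 | 9% | 0.289 | 5% | 66 |
| 0.5 | 25% | 0.262 | 13% | 80 |
| 0.7 | 49% | 0.216 | 29% | 118 |

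The proportional narrowing is close to 1 − √(1 − r²), so it hardly depends on n. The same percentages arise at 40 per arm.

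**Step 4. What pooling the pre-treatment scan would do, if it were done.** Suppose all scans were averaged with equal weight, one before treatment and m after, with the same effect at each later scan. The expected contrast is m/(m + 1) of the true effect.

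- Entry at 26 weeks, scans at about 26, 30, 34 and 38: m = 3, contrast 3/4, a loss of 25%.
- Entry at 28 weeks, scans at about 28, 32 and 36: m = 2, contrast 2/3, a loss of 33%.

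This step is conditional, because no document specifies such an average.

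**The case against.** The strongest reply is that these are endpoints added after the protocol in an exploratory Phase II trial. With 1:1 randomization an unadjusted comparison of post-treatment values is unbiased, so baseline adjustment is a refinement. That stands, and it sets the weight of the point. It is also true that the gain is negligible if the correlation is 0.3 or less, and that item 7's covariate sentence need not be read as a closed list.

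Several stronger readings are tempting, and the documents do not support them:

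- *The Doppler endpoint is diluted by the pre-treatment scan.* The four-weekly schedule is a measurement plan, not an endpoint definition. The SAP neither includes nor excludes that scan.
- *Every dyad has both baseline values.* Protocol 3.1.2 and 4.1.2 allow study drug to start off site. Obstetric ultrasound, the source of EFW, is missing from the visit lists in 4.1.1 and 4.1.2, although 3.1.2 places it at baseline. Baseline Doppler is better supported, by 5.2.2.
- *Item 7 is the only adjusted model.* Items 3 and 6d are regressions too; they simply do not use these baselines.
- *The plan loses a stated amount of power.* The t-test list in item 4 omits these endpoints. What the SAP expressly gives outcomes and neonatal characteristics is descriptive summaries, so no before-and-after power can be attributed to the plan.
- *Fetal flow is a protocol objective.* The aims and hypotheses in Protocol 2.1 and 2.2 and the endpoints in 6.1 and 6.2 do not mention it.

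**Conclusion.** The point holds as a low-cost improvement, not as an error that biases a result. Pre-treatment counterparts of Doppler flow and birthweight are planned, the SAP's covariate-adjusted model lists neither, and the scans that form the Doppler endpoint are undefined.

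The cost is precision. At 60 per arm, adjustment would narrow the 90% interval by about 2%, 5%, 13% or 29% for an assumed correlation of 0.2, 0.3, 0.5 or 0.7. Where the truth lies in that range cannot be settled from the documents. A 25% to 33% loss of contrast would follow only if the pre-treatment scan were averaged into the outcome, so it is a reason to define the endpoint and not a finding about the plan. Stating which scans count is useful whatever the correlation turns out to be.

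**What to change.** Amend the SAP wording, before treatment codes are released to those choosing the analysis:

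- **Post-protocol item 1 (Doppler flows).** Define the outcome on post-randomization gestational-age Z-scores only, either in a named gestational window or across visits. Analyze by linear regression, or a mixed model over visits, on arm, the dyad's own baseline PI Z-score and CHD stratum. Section 5.2.3 applies the Z-score conversion to the umbilical artery, ductus venosus and middle cerebral artery, so state the scale for the uterine artery as well.
- **Post-protocol item 7 (birthweight Z-score).** Add the baseline EFW Z-score as a covariate. Protocol 5.2.1 already compares EFW with published weight percentiles.
- **Missing baseline.** Keep the dyad and use a simple imputed baseline value, derived without regard to arm.

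The cost is a few lines of SAP text and no planned data beyond what the protocol already schedules. The small downside is the imputed value for dyads without a baseline scan, which gives up some of the precision gain for them.
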